5.3 Randomization and Code Breaking Procedures

The list of randomized treatment assignments stratified by gender and IL28B status will be prepared by statisticians at The Emmes Corporation and included in the enrollment module of The Emmes Corporation's Internet Data Entry System (IDES). IDES will assign each subject a treatment code from the list after demographic and eligibility data have been entered into the system. A designated individual at each site will be provided with a treatment key, which links the treatment code to the actual treatment assignment, which will be kept in a secure place.

Instructions for use of the enrollment module are included in the IDES User's Guide. Manual back-up randomization procedures are provided for use in the event that the site temporarily loses access to the Internet or the online enrollment system is unavailable.

Unblinding

Unblinding is unlikely to be necessary for the provision of medical treatment or to otherwise protect the safety of study subjects. In the event that an investigator is concerned that a subject might be put at undue risk by continuing product use, the investigator may discontinue product use by this subject; however, knowledge of the specific product (vaccine or placebo) to which the subject was assigned should not be necessary to guide further follow-up and/or treatment.

The co-principal investigators and/or Independent Safety Monitor (ISM) should be available to review and evaluate any notable reactions. In the case of a medical emergency, the co-principal investigators or ISM may deem it medically necessary to unblind the subject's treatment assignment. If the co-principal investigators or ISM believe that unblinding would benefit the medical care of the subject and time permits, DMID will be consulted prior to unblinding, and concurrence will be obtained.

Otherwise, subjects will be unblinded to their drug only at the close of the trial. Subjects who develop HCV infections or drop out will not be unblinded early. The Data Safety and Monitoring Board (DSMB) may receive data in aggregate and presented by treatment group, but without the treatment group identified. The DSMB may be unblinded to individual study treatment assignments, as needed, to adequately assess safety issues.

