11.4.5 Evaluation of Exploratory Efficacy Endpoints

1. Reduction in incidence of primary HCV infection associated with AdCh3NSmut1 and MVA-NSmut HCV vaccines

HCV RNA and and/or anti-HCV will be used to classify incident infection, using the definition described in Section 3.3 (page 20). The observed cumulative incidence of primary HCV infection in the IDU populations participating to the study has been observed at 27%/100 PYO³⁰. Analyses will be performed in both ATP and mITT populations. The analyses will be based on comparisons of incidence of HCV infection between study groups using a log-rank test for time to midpoint in both ATP and mITT populations. A sensitivity analysis will also be performed using interval censoring methods.

2. Reduction of HCV chronic infection with a 9 month chronic cut-off associated with AdCh3NSmut1 and MVA-NSmut HCV vaccines

Previous data have shown that acute HCV infection in individuals followed for two years is cleared in 86% of cases by 6 months, but in a small number, clearance occurs after 6 months (95% at 12 months³⁰). We will assess the reduction in incidence of chronic infection based on 9 months follow up after incident infection. HCV RNA assays will be used to classify chronic infections at 9 months using the definition described in Section 3.3 (page 20). Analysis will be performed in both ATP and mITT populations.

3. Reduction of peak concentration (magnitude) of HCV RNA associated with AdCh3NSmut1 and MVA-NSmut HCV vaccines

Quantitative measures of HCV RNA concentration will be compared between vaccinated and controls. We expect to observe a reduction of 3 log values of the maximum concentration of RNA detected in the blood in vaccinated subjects who develop HCV viremia (similar to that observed in subjects with HCV reinfection²⁹), compared to the placebo group. Quantitative viremia measures, including the initial peak and total HCV RNA levels (described in Section 3.3 page 20) be compared, between vaccinated and placebo arms, using logarithmic IU/mL values, by Kruskal-Wallis test, and a non-parametric equality of median tests. Analysis will performed in both on ATP, and mITT populations.

4. Reduction in the duration of HCV viremia following incidence HCV infection associated with AdCh3NSmut and MVA-NSmut HCV vaccines

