4.4.2. Method of Assigning Subjects to Treatment Groups (Randomization)

Enrollment of subjects is done online using the enrollment module of the EDC, maintained by the SDCC. Eligible subjects are randomized and assigned in a 1:1 ratio stratified by site, gender, and IL28B status, to receive AdCh3NSmut1 and MVA-NSmut HCV vaccines or placebo at Day 0 and Day 56 after providing consent and confirmation of eligibility with the study inclusion and exclusion criteria.

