6.4. Covariates and Subgroups

As described in Section 4.4.2, the randomization of treatment assignments and the primary analysis will be performed as stratified by gender and IL28B status. Randomization is also stratified by clinical site, however given that the University of New Mexico was added late in enrollment (first enrollment 16 November 2015); stratifying analyses by site in addition to gender and IL28B may result in insufficiently sized strata. Thus, efficacy analyses will not be stratified by site and safety analyses will be separately stratified by site.

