- For subjects in the ATP (mITT) cohort who develop HCV infection, the 9-month chronic infection endpoint will be coded as an observed event if the 9-month chronic infection endpoint definition is met, and as censored otherwise, with time to event defined as the elapsed time from the second (first) vaccination to the date of the sample collection with available test result nearest to the target assessment date of nine months after primary incident infection.

Kaplan-Meier curves will be presented in [Figure 7](#) and [Figure 8](#). Regression model summaries will be presented in [Table 14](#) and [Table 15](#).

Exploratory Objective 3: To determine if AdCh3NSmut1 and MVA-NSmut HCV vaccines will reduce peak concentration (magnitude) of HCV RNA compared to placebo, in blood samples of persons with incident HCV infection.

HCV RNA concentrations will be summarized by treatment group and by each month from HCV Infection for the ATP and mITT populations. Summaries will include n (number observed), minimum, maximum, geometric mean and the associated 95% confidence interval as well as geometric fold rise from the concentration at the first HCV RNA detection and the associated 95% confidence interval ([Table 16](#), [Table 17](#), [Table 18](#), [Table 19](#)). For each subject, the peak concentration from the first HCV RNA detection to the 6 month blood collection will be identified. The logarithmic peak concentrations will be compared between the vaccine and placebo groups using a two-sided t-test ([Table 20](#) and [Table 21](#)).

Exploratory Objective 4: To determine if AdCh3NSmut1 and MVA-NSmut HCV vaccines will reduce duration of HCV viremia (shorter time to spontaneous resolution) during incident infection (6-month period following incident HCV infection) compared to placebo in blood samples of persons with incident HCV infection.

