The duration of incident infection (time to spontaneous resolution) is expected to decrease 4-fold in vaccinated subjects who develop viremia (similar to that observed in subjects with HCV reinfection), compared to the placebo group, after 6 months of observation following incident infection. The midpoint between infection and clearance dates will be used to determine duration as previously described (Section 3.3.5). For subjects without observed clearance, the resolution endpoint will be coded as censored, with time to event defined as the elapsed time from the incident infection, to the end of the 6 month follow up, or to the last observed visit before loss to follow-up or to the earliest time any criterion listed under the censoring criteria for the ATP (or mITT) cohort was met.

Analyses of this objective will follow the proportional hazards analysis plan for the primary outcome. Kaplan-Meier curves will be presented in [Figure 9](#) and [Figure 10](#). Regression model summaries will be presented in [Table 22](#) and [Table 23](#). Summary statistics of duration will be presented in [Table 24](#).

Exploratory Objective 5: To determine if AdCh3NSmut1 and MVA-NSmut HCV vaccines will reduce incidence of chronic HCV infection with genotype 1 compared to non-genotype 1 among HCV-uninfected IDU.

A chronic HCV infection genotype 1 will be defined as a chronic HCV infection at 6 months, as defined in Section 3.3.2, with the additional requirement that the infection is genotype 1 as determined from blood samples obtained at the first HCV viremic visit, provided sufficient sample is available.

Because the vaccine is developed from HCV genotype 1b sequences, we hypothesize that we may see greater reduction in chronic infection with HCV genotype 1, compared to other genotypes as a result of stronger genotype specific immune responses: 75% reduction in chronic infection with genotype 1 compared to 45% reduction in chronic infection with non-1 genotypes. These exploratory analyses will be based on estimates of the incidence of HCV genotype 1 infection and non-1 genotypes in each study group using methods for censored survival regression with competing risks (Fine-Gray proportional hazards).

Analyses of this objective will follow the Fine-Gray proportional hazards analysis plan for the Primary Efficacy Objective where two separate models will be fit:

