n = number of HCV-infected subjects with HCV RNA data available after incident infection in the analysis population.
P-value = p-value from two-sided t-test

Tables with similar format:

Table 21: Geometric Mean (GM) Peak HCV RNA Concentrations with 95% Confidence Intervals by Treatment Group— mITT Population

Table 22: Vaccine Efficacy Against Duration of Incident HCV Infection by Treatment Group and Analysis Population

Analysis	Analysis Population	Number of Incident HCV Infections		Vaccine Efficacy [1]	95 % CI for Vaccine Efficacy [2]	P-value [3]
		Vaccine (N=X)	Placebo (N=X)			
Primary Efficacy Analysis	ATP population	x	x	x.xx	x.xx, x.xx	0.xxx
Secondary Efficacy Analysis	mITT population	x	x	x.xx	x.xx, x.xx	0.xxx

Notes: N = Number of subjects in specific treatment group.
 [1] Vaccine efficacy is obtained from stratified Cox regression.
 [2] 95% CI = 95% confidence interval obtained from stratified Cox regression.
 [3] P-value = p-value from score test comparing treatment groups obtained from stratified Cox regression (log-rank test).

Table 23: Stratum-Specific Vaccine Efficacy Against Duration of Incident HCV Infection by Treatment Group and Analysis Population

Analysis		Number of Incident HCV Infections		Vaccine Efficacy [1]	95 % CI for Vaccine Efficacy [2]	P-value [3]
		Vaccine (N=X)	Placebo (N=X)			
ATP Population	All subjects	x	x	x.xx	x.xx, x.xx	0.xxx
	Males	x	x	x.xx	x.xx, x.xx	0.xxx
	Females	x	x	x.xx	x.xx, x.xx	0.xxx
	CC	x	x	x.xx	x.xx, x.xx	0.xxx
	CT/TT	x	x	x.xx	x.xx, x.xx	0.xxx
mITT Population	All subjects	x	x	x.xx	x.xx, x.xx	0.xxx
	Males	x	x	x.xx	x.xx, x.xx	0.xxx
	Females	x	x	x.xx	x.xx, x.xx	0.xxx
	CC	x	x	x.xx	x.xx, x.xx	0.xxx
	CT/TT	x	x	x.xx	x.xx, x.xx	0.xxx

Note: N = Number of subjects in specific treatment group.
 [1] Vaccine efficacy is obtained from stratified Cox regression.
 [2] 95% CI = 95% confidence interval obtained from stratified Cox regression.
 [3] P-value = p-value from score test comparing treatment groups obtained from stratified Cox regression.

Table 24: Summary Statistics of Duration of Incident HCV Infection by Treatment Group and Analysis Population

Statistic	ATP Population		mITT Population	
	Vaccine (N=X)	Placebo (N=X)	Vaccine (N=X)	Placebo (N=X)
Mean	x.x	x.x	x.x	x.x
Standard Deviation	x.x	x.x	x.x	x.x
Median	x.x	x.x	x.x	x.x
Minimum	x	x	x	x
Maximum	x	x	x	x

Table 25: Vaccine Efficacy Against 6-Month Chronic HCV Genotype 1 Infection by Treatment Group and Analysis Population

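### Peak HCV RNA (Exploratory Objective 3): the unadjusted t-test is valid, but an estimate adjusted for gender and IL28B should be added

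*SAP*

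**What the plan says.** **The test.** SAP 8.3, Objective 3, takes each infected subject's highest HCV RNA from first detection to the 6-month sample. "The logarithmic peak concentrations will be compared between the vaccine and placebo groups using a two-sided t-test". The shells for Tables 20 (ATP) and 21 (mITT) give n, geometric mean and 95% CI for each arm, with one p-value, footnoted "P-value = p-value from two-sided t-test". They have no stratum rows, no adjusted result, and no between-arm ratio or interval.

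**The randomisation.** Protocol 5.3 refers to "The list of randomized treatment assignments stratified by gender and IL28B status". SAP 4.4.2 adds site: "Eligible subjects are randomized and assigned in a 1:1 ratio stratified by site, gender, and IL28B status". SAP 6.4 says that "the randomization of treatment assignments and the primary analysis will be performed as stratified by gender and IL28B status", and drops site from the efficacy models because New Mexico joined late and strata could become too small.

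**The neighbouring objectives.** Objective 1 uses a Cox model stratified by the four gender-by-IL28B cells, and Objective 2 repeats the primary analysis. For Objective 4, duration of viremia in infected subjects: "Analyses of this objective will follow the proportional hazards analysis plan for the primary outcome". That objective also has a stratum-specific table (Table 23). Objective 5 follows the Fine-Gray plan, which includes a stratified version.

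**The protocol's test for this endpoint.** Protocol 11.4.5 compares initial peak and total RNA "using logarithmic IU/mL values, by Kruskal-Wallis test, and a non-parametric equality of median tests". These tests are also unadjusted. SAP Section 14 does not record the change of test or the loss of the between-arm comparison of total RNA.

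**The concern.** Objective 3 is the only exploratory efficacy objective whose planned comparison leaves out gender and IL28B. It is run only in subjects who become infected. Stratified randomisation balances the enrolled cohort and does not guarantee balance in that subset.

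Two things are at stake, both modest. If either factor is related to peak RNA, the variance it explains stays in the error term. And if one arm's infected subjects include more of one IL28B type by chance, the report would hold no estimate that takes this into account. Objective 4 uses the strata in the same subset, and the SAP gives no reason for treating peak RNA differently.

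**Working it through.** **1. Inputs from the documents.** ATP cohort of 292.5 subjects followed for 1.5 years (SAP 5); primary infection at 27 per 100 person-years, and an expected 3 log reduction in peak RNA (both Protocol 11.4.5); two-sided 5% level (SAP 8). The documents give no SD, sample size or power for Objective 3. The one design figure available is for the primary endpoint, and it reproduces:

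- Events needed: 4(1.960 + 1.036)² / (ln 0.40)² = 42.8, so 43.
- Events expected: (292.5/2) × 1.5 × (0.14 + 0.056) = 43.0.

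**2. Assumed, because the documents are silent.** Share of variance in log peak RNA explained by the strata (R²): 0 to 0.20. SD of log10 peak RNA: 1 to 2. IL28B CC prevalence: 40%.

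**3. Infected per arm.**

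- No effect on acquisition: 146.25 × (1 − exp(−0.27 × 1.5)) = 48.7, about 50.
- Acquisition also falls 60% in the vaccine arm (assumption): 146.25 × (1 − exp(−0.405 × 0.4)) = 21.9 in that arm.

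I therefore use 50 and 20 per arm.

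**4. Effect of adjustment on the standard error.** With N infected in total and q covariate terms:

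SE ratio (adjusted/unadjusted) = √[(1 − R²)(1 + q/(N − q − 3))]

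Using q = 3 (all four gender-by-IL28B cells), the second factor is 1 + 3/94 = 1.032 at N = 100 and 1 + 3/34 = 1.088 at N = 40.

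| R² | 50 per arm | 20 per arm |
|---|---|---|
| 0 | 1.016 | 1.043 |
| 0.05 | 0.990 | 1.017 |
| 0.10 | 0.964 | 0.990 |
| 0.20 | 0.909 | 0.933 |

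The model proposed below has only two extra terms. At R² = 0 and 50 per arm it costs √(1 + 2/95) = 1.010, so the table slightly overstates the price.

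**5. Power.** At 50 per arm, a 1 log difference and SD 1.5, power is 0.915 unadjusted. Adjusted, it is 0.907, 0.920, 0.933 and 0.956 for R² of 0, 0.05, 0.10 and 0.20. At 3 log, power is at least 0.995 either way for 20 to 50 per arm and SD 1 to 2.

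**6. Chance IL28B imbalance.** SD of the difference in CC share = √(2 × 0.4 × 0.6/n).

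- n = 50: SD 0.098, 95% limit ±19 points. If IL28B shifts peak RNA by 0.25, 0.5 or 1 log (assumed), the arm difference moves by up to 0.05, 0.10 or 0.19 log.
- n = 20: SD 0.155, 95% limit ±30 points. The shifts are 0.08, 0.15 and 0.30 log.

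**7. Simulation** (4,000 trials per scenario; stratified randomisation of 292, about one third infected at random in both arms, SD 1.5; t-test against a four-cell linear model). Neither method was biased. Type I error was 0.044 to 0.047 for the t-test and 0.045 to 0.047 adjusted. Power at a 1 log difference:

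| Assumed IL28B / gender effect (log) | t-test | Adjusted |
|---|---|---|
| 0 / 0 | 0.898 | 0.888 |
| 0.5 / 0.25 | 0.884 | 0.882 |
| 1 / 0.5 | 0.858 | 0.886 |

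A setting more favourable to adjustment (SD 1, true effect 0.5 log, gender and IL28B as main effects) gave 68.4% against 67.7% with no factor effects. With 1.0 log for IL28B and 0.5 log for gender it gave 57.4% against 67.5%.

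**The case against.** The other side has a strong case, and most of it stands. The endpoint is exploratory. SAP 6.4 promises gender and IL28B stratification for the primary analysis only. The objectives that do stratify are all time-to-event, and the protocol's own tests for peak RNA are unadjusted. No commitment is broken. The protocol expects a 3 log difference, against which a shift of 0.05 to 0.30 log is small.

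A reader might infer several stronger things that the documents do not support:

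- **That the t-test is biased or invalid.** Chance imbalance is part of the sampling variation that its standard error already reflects, and the simulation shows no bias and no inflation of type I error.
- **That it certainly loses precision.** With R² near zero, adjustment costs a little.
- **That IL28B was made a stratum because it predicts HCV outcome.** The documents state the stratification without giving that reason, and link neither factor to peak RNA.
- **That a planned interval is too wide.** Tables 20 and 21 plan no between-arm interval.
- **That adjustment would make the infected arms comparable.** Infection occurs after randomisation. If the vaccine changes who becomes viremic, the resulting selection is not removed by adjusting for two baseline factors.

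What remains is the omission itself: no adjusted estimate is planned for this endpoint, although the SAP uses the strata for Objective 4 in the same subjects.

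**Conclusion.** The point holds as a small improvement in efficiency and interpretability. At about 50 infected per arm, the standard error moves from about 1.6% larger (R² = 0) to 4% smaller (R² = 0.10) or 9% smaller (R² = 0.20). At 20 per arm the break-even R² lies between 0.05 and 0.10. These figures rest on assumed R², SD and CC prevalence.

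If the 3 log reduction occurs, the test result is the same with or without adjustment. Adjustment could matter for a true difference nearer 0.5 to 1 log with strongly prognostic factors. Even then it sharpens a valid analysis and does not repair a faulty one.

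**What to change.** Before unblinding, add to SAP 8.3 Objective 3 a linear model of log10 peak HCV RNA on treatment, gender and IL28B (CC vs CT/TT), fitted in the ATP and mITT populations. Omit site, in line with SAP 6.4. Add to Tables 20 and 21 the adjusted vaccine/placebo geometric mean ratio with 95% CI and p-value, and keep the unadjusted test as a supporting line. If the protocol's non-parametric approach is kept, use a stratified rank test instead; SAP 11 already uses Van Elteren's test for the behaviour data. State in the text that the comparison is conditional on infection and that the adjustment does not remove selection. The same edit is a convenient place to record in Section 14 the move away from the protocol's tests and the missing total-RNA comparison.

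The cost is a short SAP edit and one model per population, using factors already collected. The statistical price is about two degrees of freedom, which is negligible if neither factor is prognostic.

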11.4.3 Evaluation of the Primary Efficacy Endpoint

Reduction in the incidence of chronic HCV infection associated with AdCh3NSmut1 and MVA-NSmut HCV vaccines.

HCV RNA assays will be used to classify chronic vs. cleared infection, using the definition described in Section 3.1.2 (page 19). Based on previous analysis performed in IDU cohorts in Baltimore and San Francisco, we expect very few cases of re-infection to occur during the trial time.^{29,30} Blood samples from individuals who demonstrate alternating positive and negative HCV RNA results, suggestive of reinfection will be analyzed to determine infection status using genotyping tests and viral sequencing where necessary to confirm infection outcome. A small number of cases may occur in which individuals will clear HCV viremia after 6 months of infection. All possible cases, including cases with uncertain classification for chronicity, will be reviewed by a blinded independent case review committee to make a determination of infection outcome.

The primary efficacy analysis will be performed in the ATP cohort, and repeated in the mITT cohort, as defined in Section 11.4.1 above. A time to event analysis will be performed as follows. For subjects in the mITT (ATP) cohort without acute HCV

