3.2. Endpoints

The primary safety endpoints are as follows:

1. Occurrence of vaccine-related serious adverse events (SAEs) from the time of first vaccination through the entire study period.
2. Occurrence of severe local and/or systemic solicited reactogenicity signs and symptoms in the 8 days (Day 0-7) after each vaccination.
3. Occurrence of clinical safety laboratory adverse events (AEs) assessed at baseline and 1 month following each vaccination.

The occurrence of these safety parameters will be assessed by treatment group (vaccine and placebo).

The primary efficacy endpoint is:

1. Chronic HCV infection at 6 months defined by persistent viremia over a period of 6 months after detection of incident infection.

The secondary immunogenicity endpoint is:

1. The frequency of positive cell mediated immune response within 14 days after the last vaccination by treatment group (vaccine vs. placebo)

The exploratory efficacy endpoints are as follows:

1. An incident HCV infection will be defined as a new confirmed positive HCV RNA test after a previous negative HCV RNA test. The interval during which incident HCV infection occurs will be defined by the date of the last documented negative HCV RNA results, and the date of the first positive HCV RNA result.
2. Chronic HCV infection at 9 months defined by persistent viremia over a period of 9 months after detection of incident infection.
3. Quantitative viremia measures, including the incident peak and total HCV RNA levels detected, from the date of first HCV RNA detection and at study visits in the first 6 months of viremia will be compared, between vaccinated and placebo groups, using logarithmic IU/mL values.
4. The duration of incident infection will be defined as the interval between incident HCV infection and viral clearance. For subjects who do not clear HCV viremia, the duration will be measured as six months following incident infection. The interval during which incident HCV infection occurs will be defined by the date of the last documented HCV RNA negative results, and the date of the first positive HCV RNA result. The interval during which viral clearance occurs will be defined by the date of the last test with detectable HCV RNA and the first of two consecutive samples with undetectable HCV RNA.

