3.3.5. Duration of Incident Infection

The duration of incident infection will be defined as the midpoint of the interval between incident HCV infection and viral clearance. The incident HCV infection date will be defined as the midpoint of the interval between the date of the last documented HCV RNA negative result and the date of the first positive HCV RNA result. The viral clearance date will be defined as the midpoint of the interval between the date of the

last test with detectable HCV RNA and the first of two consecutive samples with undetectable HCV RNA. For subjects who do not clear HCV viremia, the duration will be measured as six months following incident infection for the fourth exploratory endpoint.

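### Exploratory Objective 4 censors non-clearers at six months but sets no six-month limit on clearers, so any arm with a late clearer gets a Kaplan-Meier curve that ends at zero

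*SAP*

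**What the plan says.** SAP 8.3, Exploratory Objective 4, analyses time to resolution with Kaplan-Meier curves (Figures 9 and 10), the Cox models used for the primary outcome (Tables 22 and 23) and summary statistics of duration (Table 24).

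- **Non-clearers.** "For subjects without observed clearance, the resolution endpoint will be coded as censored", with time running "to the end of the 6 month follow up, or to the last observed visit before loss to follow-up" or to a cohort censoring criterion. SAP 3.2 and 3.3.5 match this: "For subjects who do not clear HCV viremia, the duration will be measured as six months following incident infection for the fourth exploratory endpoint".
- **Clearers.** Clearance is dated to the midpoint between the last detectable sample and "the first of two consecutive samples with undetectable HCV RNA" (SAP 3.3.5). No upper time limit is given in 3.2, 3.3.5 or 8.3.
- **Sampling.** Viremic subjects have monthly quantitative RNA at H01 to H09, that is to month 9 (Protocol 8.3 and Appendix D; SAP 4.1 and Table 2).
- **Late clearance is expected.** Protocol 11.4.3: "A small number of cases may occur in which individuals will clear HCV viremia after 6 months of infection". Protocol 11.4.5 says that infection "is cleared in 86% of cases by 6 months, but in a small number, clearance occurs after 6 months", and gives 95% at 12 months.

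**The concern.** The six-month limit depends on the outcome. A subject still viremic at month 9 is censored at month 6. A subject who clears at month 8 has an observed clearance and, as written, stays at risk until month 8. After month 6 the risk set therefore holds only people who will clear.

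Two outputs suffer. The Kaplan-Meier curve must end at zero in an arm with a late clearer, while an arm without one keeps its plateau. Side by side, the two tails could be mistaken for a difference between arms. In Table 24, a subject who eventually cleared can have a longer duration than one who never did.

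**Working it through.** The documents give no event count or power for Objective 4, so there is no figure to reproduce. The rule is applied directly.

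**1. When can a late clearance be dated?** Take visits on target, so that the infection date is 15 days before the first positive sample, and six months = 180 days. Duration = midpoint of the last detectable and first undetectable days, plus 15.

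| First undetectable | Confirmed at | Duration |
|---|---|---|
| H06 | H07 | (150+180)/2 + 15 = 180 d |
| H07 | H08 | (180+210)/2 + 15 = 210 d |
| H08 | H09 | (210+240)/2 + 15 = 240 d |

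Two consecutive undetectable samples are needed and scheduled visits end at H09, so late clearances date to about months 7-8.

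**2. Effect on the curve and on Table 24.** Assume an arm of 30 infected subjects. Eight clear by month 6, at days 30, 60, 60, 90, 90, 120, 150 and 180 (sum 780). Each late clearer replaces one non-clearer.

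| Late clearers | Final S, as written | Mean duration, as written | Maximum |
|---|---|---|---|
| none | 22/30 = 0.733 | (780 + 22×180)/30 = 158.0 d | 180 d |
| one (210 d) | 0.733 × (1 − 1/1) = 0 | (780 + 210 + 21×180)/30 = 159.0 d | 210 d |
| two (210, 240 d) | 0.733 × 1/2 = 0.367, then 0 | (780 + 450 + 20×180)/30 = 161.0 d | 240 d |

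With clearances after day 180 censored at day 180, all three rows give S = 0.733, mean 158.0 d and maximum 180 d. The median is 180 d throughout.

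**3. How often would an arm be affected?** Read the protocol's 86% and 95% as shares of eventual clearances, spread evenly over months 6-12. Months 6-8 then hold (0.95 − 0.86) × 2/6 = 0.03 of them. With n infections and a proportion p clearing, the chance of at least one late clearer is 1 − (1 − 0.03p)^n. Neither n nor p is given for this endpoint. Protocol 2.1 puts spontaneous resolution at about 20%. The incidences of 27 and 14 per 100 person-years in Protocol 11.4.5 and 11.2 would imply about 1 − 14/27 = 48%.

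| Infections per arm (assumed) | p = 20% | p = 30% | p = 50% |
|---|---|---|---|
| 20 | 11% | 17% | 26% |
| 40 | 21% | 30% | 45% |
| 60 | 30% | 42% | 60% |

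At 40 infections, the expected number of late clearers is 40 × p × 0.03 = 0.24, 0.36 or 0.60 per arm.

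**4. Effect on the Cox model.** Up to month 6 the risk sets are the same with or without a cap. After month 6, an event contributes exp(βx_i) / Σ exp(βx_k), summed over those at risk in the stratum. If those at risk all belong to one arm, this does not involve β. A late event matters only when late clearers from both arms are at risk together in the same one of the four gender-by-IL28B strata.

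An unstratified simulation (60 infected per arm, 600 trials per setting, exponential clearance times with 86% of clearances by month 6) gave:

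| True clearance HR; p in placebo | Late clearers per trial | Mean HR, as written / capped | Rejection rate, as written / capped |
|---|---|---|---|
| 1; 30% | 2.05 | 1.01 / 1.01 | 0.042 / 0.040 |
| 2; 30% | 2.52 | 2.00 / 2.03 | 0.610 / 0.618 |
| 4; 30% | 2.80 | 3.92 / 4.02 | 1.000 / 1.000 |
| 1; 48% | 2.89 | 0.99 / 0.99 | 0.057 / 0.065 |

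The first setting has about twice the late clearers implied by step 3 (120 × 0.30 × 0.03 = 1.08), so it leans towards finding an effect.

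**5. The midpoint wording.** SAP 3.3.5 defines duration itself as the midpoint of the interval between infection and clearance, and 8.3 repeats this. SAP 3.2 and Protocol 3.3 define it as the interval. Taken literally, the 240-day clearance becomes an event at 240/2 = 120 days, or month 4, although that subject was viremic at month 6. The drop to zero disappears, but a late clearance is counted inside the window and every clearer's duration is halved.

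**The case against.** The best defence is intent. The objective is framed as a six-month period after incident infection, and 8.3 calls the endpoint's follow-up six months long. On that reading, lacking an observed clearance means lacking one within six months, and the month-8 clearer is censored too. This probably is what was meant, so the problem is a missing rule, not a plan to analyse months 6-9. But no operative sentence says so. Objective 3, in the same section, does state its limit for each subject, ending at the 6-month blood collection. A programmer following Objective 4 as written would code a month-8 clearance as an event at month 8.

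A second defence is that the literal midpoint rule leaves no event after month 6. That is true, but step 5 shows that it only moves the error.

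Three stronger readings are tempting, and the documents do not support them:

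- *The curves will fall to zero.* This happens only in an arm with at least one late clearer. At 40 infections per arm, 55-79% of arms would have none.
- *The estimated vaccine effect is distorted.* The hazard ratio and the test hardly move (step 4). Only the tail of a figure could mislead.
- *Table 24 is invalid.* It is descriptive. In the worked arm, one late clearer moves the mean by 1 day and leaves the median alone. The maximum does change, and the ordering is wrong for that subject.

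**Conclusion.** The concern holds as a gap in the rule for an exploratory endpoint. Non-clearers leave at six months, and nothing stops a clearance dated to about 7-8 months from counting as an event. In an arm where that occurs, Figures 9-10 end at zero and Table 24 gives that subject 210-240 days against 180 for someone who never clears.

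The chance is about 21%, 30% or 45% per arm. This rests on 40 infections per arm, on 20%, 30% or 50% clearing, on the reading of the 86% and 95% figures, and on an even spread of late clearances. Clearances bunched soon after month 6 would raise it. The effect on Tables 22-23 is negligible, and the primary, safety and immunogenicity analyses are untouched. It is a minor correction, but a cap is needed under either reading of duration.

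**What to change.** State in SAP 3.3.5 and in 8.3, Objective 4: *Follow-up for this endpoint ends six months after incident infection for all subjects; a subject whose clearance date is later is censored at six months.* Then:

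- Restrict Figures 9-10 to 0-6 months.
- Correct the midpoint wording in 3.3.5 and 8.3, so that duration is the interval from the infection date to the clearance date, each of those dates being a midpoint between samples.
- Compute Table 24 on the capped durations, optionally adding the six-month restricted mean. Do not rely on a Kaplan-Meier median. With 20%, 30% or 50% clearing, the proportion still viremic at month 6 is 1 − 0.86p = 83%, 74% or 57%, so the median would usually not be reached.

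The cost is one added rule and one truncation step in the derivation. Clearances after month 6 no longer count for this endpoint, but Exploratory Objective 2 still covers the nine-month outcome.
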